8.2 Estimation of sample size

Sample size estimation is primarily based on the study 3119001 LEVALS SVC (supine) results (Table 6). The LEVALS study had placebo controlled data only up to 2 weeks and therefore extrapolation of the results is needed. The placebo effect from phase II tirasemtiv trial BENEFIT-ALS (Shefner JM et al., 2016) is also evaluated.

Assuming at least 3.6% difference between treatment arms and common standard deviation of 10%, 164 evaluable subjects have 90% power to detect a statistically significant difference at two-sided 5% level using 1:1 allocation ratio and two group T-test. Randomisation of 450 subjects to study using a 2:1 allocation ratio (approximately 300 levosimendan and 150 placebo treated subjects) allows approximately 20% drop out rate.

Based on dexpramipexole phase III study EMPOWER (Cudkowicz ME et al., 2013) 12 point reduction in total ALSFRS-R score and a 15% mortality rate at 12 months can be assumed in placebo treated patients. Assuming 10 point decline, with 8 point standard deviation, in ALSFRS-R and 20% relative improvement in survival 450 patients provide approximately 80% simulated power to detect statistically significant difference using joint rank test. With 450 subjects and assuming 48 week levosimendan event rate of 73% and hazard ratio of 0.70, time to respiratory event has approximately 70% power to detect statistically significant difference using log-rank test.

Table 6.	Mean ((SD)	change fi	rom base	line	SVC ((supine)

Treatment	2 weeks	12 weeks
Levosimendan 1 mg x 2	+2.4 (8.3)	-4.9
Levosimendan 1 mg x 1	+0.8 (8.6)	
Placebo	-3.6 (9.4)	-17.7 ¹
Placebo (BENEFIT-ALS)	-1.4	-8.5

¹ Extrapolated from the data

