5. DETERMINATION OF SAMPLE SIZE

Sample size estimation is based primarily on supine SVC results from the study 3119001 LEVALS (Table 1). LEVALS had placebo-controlled data only up to 2 weeks, and therefore extrapolation of the results was needed. The placebo effect from phase II tirasemtiv trial BENEFIT-ALS (Shefner JM et al., 2016) was also evaluated.

Assuming a difference of at least 3.6% in change from baseline supine SVC between treatment groups and a common standard deviation of 10%, 164 evaluable subjects per group in a 1:1 allocation ratio have 90% power to detect a statistically significant difference in a two-sided, 5% α -level, two group T-test. Using a 2:1 allocation ratio, randomisation of 450 subjects to the study (approximately 300 levosimendan and 150 placebo treated subjects) allows for a total dropout rate of approximately 20%.

Table 1. Mean (SD) change from baseline SVC (supine) %-predicted in LEVALS

Treatment	2 weeks	12 weeks
Levosimendan 1 mg x 2	+2.4 (8.3)	-4.9
Levosimendan 1 mg x 1	+0.8 (8.6)	
Placebo	-3.6 (9.4)	-17.7 ¹
Placebo (BENEFIT-ALS)	-1.4	-8.5

¹ Extrapolated from the data

SD = standard deviation

Based on the dexpramipexole phase III study EMPOWER (Cudkowicz ME et al., 2013), a 12 point reduction in total ALSFRS-R score and a 15% mortality rate at 12 months can be assumed

in placebo treated patients. Assuming a 10 point decline in ALSFRS-R, with a standard deviation of 8 points, and a 20% relative improvement in survival, 450 patients provide approximately 80% simulated power to detect a statistically significant difference using a joint rank test. With 450 subjects and assuming a 48-week levosimendan event rate of 73% and hazard ratio of 0.70, time to respiratory event has approximately 70% power to detect a statistically significant difference using a log-rank test.

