Tipping point analyses will be considered for further evaluating sensitivity of the results with respect to missing data. In such an analysis, the distribution of missing data in the active treatment group would be shifted by varying amounts, until a point is found where the results of the analysis cross the threshold of statistical significance specified in section 6.2.2. The plausibility of a shift of the found size is then used to assess the robustness of results to unobserved differences due to missing data.

Subjects who discontinue study treatment but remain in the study can continue to contribute ALSFRS-R data, which will be included in the analyses where applicable. However, in time-to-

event analyses subjects will be censored from follow-up one day after study treatment discontinuation.

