6.2.13 Interim analyses and data monitoring

Two interim analyses will be conducted: first when approximately 50% of the subjects, and second when all of the subjects have completed their Week 12 study visit (Visit 5).

An independent DSMB will perform and evaluate the interim/futility analyses and make recommendations for the study conduct. The DSMB will have access to the treatment code through an independent reporting statistician, and the DSMB will have a possibility review any unblinded information in a separate closed session. Details on the composition and responsibility of the DSMB are outlined in a DSMB charter. Based on the futility analyses the DSMB will give its recommendation “continue” or “not continue” the study to the Orion Executive Committee (OEC).

Futility will be evaluated in the primary efficacy endpoint, and the time to respiratory event endpoint. We estimate that approximately 40% and 85% of the respiratory events will have accumulated at the time of the planned interim analyses.

In addition the SVC and respiratory event endpoints, accumulated data for the ALSFRS-R, CGI and Borg CR 10 will be summarized at the interim analyses.

Non-binding stopping criteria will be based on O’Brien-Fleming type boundaries (Lan GKK et al., 1983, O’Brien PC et al., 1979) and are detailed in the DSMB SAP.

As the interim analyses only allow early stopping for futility, not for efficacy or sample size re-estimation, adjustments to significance levels are not made in the final analyses.

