7.5.2.3 Respiratory event and other time-to-event endpoints

A 'time to respiratory event' composite endpoint consists of the following events:

- A decrease of one or more points from baseline in any of the ALSFRS-R respiratory function subdomain scores (items 10–12).
- Starting non-invasive mask ventilation (NIV).
- Meeting 'protocolised' criteria for NIV: SVC (supine) $\leq 50\%$ predicted.
- Invasive mechanical ventilation by intubation.
- Invasive mechanical ventilation by tracheostomy.
- Death.

Time to respiratory event is reached whenever any of the criteria has first been met.

The following time-to-event secondary efficacy variables will be evaluated using Cox's proportional hazards regression:

1. Time to tracheostomy, continuous ventilator dependence, or death (TRCVDDTH)
2. Time to NIV or death (NIVDEATH)
3. Time to respiratory event (RESPEVNT)

Individual components of all the composite endpoints will be analysed in the same fashion:

1. Time to continuous ventilator dependence (ALSFRS-R item 12 ≤ 1 ; CVD)
2. Time to decline from baseline in any ALSFRS-R respiratory domain score (FRSBR1D)
3. Time to SVC (supine) $\leq 50\%$ of predicted (SVC50PP)
4. Time to non-invasive mask ventilation (NIV)
5. Time to intubation (INTUB)
6. Time to tracheostomy (TRACH)
7. Time to death (DEATH)

As will these additional endpoints derived from the SVC and ALSFRS-R values:

1. Time to decline from baseline SVC (supine) by $\geq 20\%$ (SVC20PD)
2. Time to decline from baseline ALSFRS-R total score by $\geq 20\%$ (FRS20PD)
3. Time to continuous use of NIV during the night (ALSFRS-R item 12 ≤ 2)

The data for the time-to-event variables will be stored in the ADTTE dataset with parameter names corresponding to those in parentheses above.

The analysis model will include an effect for treatment, and will be adjusted for randomization strata. Premature discontinuations will be treated as right-censored in the analyses. Censoring rules for different scenarios are described in **Error! Reference source not found..** For the purpose of determining the end date, survival and ventilation status are considered to be assessed daily; ALSFRS-R and SVC measurements are assessed only on study visits. For composite

endpoints, the date of last assessment is defined to be the latest date at which the endpoint can be fully assessed: that is, the earliest date in the set of latest assessments of each of its component endpoints.

Table 2. Censoring rules for time-to-event analyses.

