Scenario	Censored	End date
Event criteria fulfilled	No	Date of endpoint assessment
Event criteria fulfilled at baseline	Yes	Date of randomization
Event criteria never assessed	Yes	Date of randomization
Completed Week 48 without event	Yes	Date of last endpoint assessment
Discontinued study	Yes	Date of last endpoint assessment
Discontinued study treatment (1 day after*)	Yes	Date of last endpoint assessment
Died, when death not part of event criteria	Yes	Date of last endpoint assessment
Died, when death is part of event criteria	No	Date of death

*) to account for potential events following immediately after the study treatment discontinuation.

SAS code in the following fashion will be used to fit the statistical models:

```
proc phreg data = ADTTE;
  where ITTFL = "Y" and PARAMCD = "RESPEVNT";
  class TRTP(ref = "PLACEBO") STRATAR;
  model AVAL * CNSR(1) = TRTP STRATAR / ties = efron rl;
run;
```

For descriptive purposes, Kaplan-Meier survival curves will be plotted in addition to the statistical analysis results from the Cox models. Also, restricted mean survival time (RMST) will be described graphically at 14-day intervals from start of follow-up up to 48 weeks. These analyses are used to visually inspect the plausibility of the proportional hazards assumption.

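### The 70% power quoted for time to respiratory event does not follow from its own inputs, which give about 88%

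*SAP*

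**What the plan says.** SAP section 5 gives the power for the second-ranked secondary endpoint in one sentence: with 450 subjects, "assuming a 48-week levosimendan event rate of 73% and hazard ratio of 0.70, time to respiratory event has approximately 70% power" using a log-rank test. Protocol 8.2 has the same calculation ("With 450 subjects and assuming 48 week levosimendan event rate of 73% and hazard ratio of 0.70") and the same 70%.

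Other parts of the plan that bear on the figure:

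- Allocation is 2:1, about 300 levosimendan and 150 placebo (SAP section 5).
- Tests are two-sided at 5%, with no adjustment for the futility looks (SAP 6.2.2).
- The only loss rate in either document is in the SVC part of SAP section 5, where 450 randomised "allows for a total dropout rate of approximately 20" per cent. Protocol 8.2 has the same allowance. It is not attached to the respiratory endpoint.
- In time-to-event analyses "subjects will be censored from follow-up one day after study treatment discontinuation" (SAP 6.2.5). For composite endpoints "the date of last assessment is defined to be the latest date at which the endpoint can be fully assessed" (SAP 7.5.2.3).
- SAP Table 2 has a row for "Event criteria fulfilled at baseline": such subjects are censored at randomisation and contribute no event.

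Neither document gives an expected share for the last two censoring routes.

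**The concern.** A 48-week event rate of 73% in the better arm means that most of the 450 subjects have an event. With a hazard ratio of 0.70, that many events should give power well above 70%. The gap is too wide for the word approximately to cover.

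The figure matters because time to respiratory event is second in the testing hierarchy and one of the two futility endpoints (SAP 6.2.13), and a reader cannot reproduce it. If the inputs are right, the plan understates its own power. If 70% is right, it rests on a loss of more than a third of the events, or on a different rate, hazard ratio, alpha or test, and the plan does not disclose it. In that case the expected event count is also far from what the stated rates imply.

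**Working it through.** **Inputs.** N = 450, split 300/150; levosimendan 48-week event rate 73%; HR 0.70; log-rank test (SAP section 5, Protocol 8.2). Two-sided 5% (SAP 6.2.2).

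**Check of method on the neighbouring figure.** For SVC (difference 3.6, SD 10), 164 per group gives z = 3.6/(10 × √(2/164)) = 3.26 and power Φ(3.26 − 1.96) = 90.3%. At 240/120, which is 450 less 20%, power is 89.6%. The SVC statement reproduces.

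**Placebo rate under proportional hazards.** Cumulative hazard on levosimendan = −ln(0.27) = 1.309. On placebo = 1.309/0.70 = 1.870, so the placebo event rate is 1 − exp(−1.870) = 84.6%.

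**Expected events.** 300 × 0.73 + 150 × 0.846 = 345.9, or 77% of 450. Because 73% is a 48-week rate, administrative censoring at week 48 is already included.

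**Power (Schoenfeld).** The allocation factor is (2/3)(1/3) = 2/9 and |ln 0.70| = 0.3567.

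z = √(345.9 × 2/9) × 0.3567 = 8.767 × 0.3567 = 3.13; power = Φ(3.13 − 1.96) = **87.8%**.

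Other methods on the same inputs agree: Freedman 90.8%, exponential Wald test 89.2%, simulated log-rank 89.1%.

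**Events needed for 70%.** (0.524 + 1.960)² / (2/9 × 0.3567²) = 218.3, or 49% of 450. The outright loss required is 1 − 218.3/345.9 = 36.9%.

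**Effect of loss.** For exponential dropout with cumulative hazard d over 48 weeks, events per subject = h/(h + d) × (1 − exp(−(h + d))). Loss rates above 20% are assumptions used to find where 70% is reached.

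| Loss | Events | Power |
|---|---|---|
| None | 346 | 87.8% |
| 20% exponential dropout | 318 | 85.1% |
| 20% removed outright | 277 | 79.9% |
| 60% exponential dropout (assumed) | 252 | 76.1% |
| One third removed (assumed) | 231 | 72.4% |
| 75% exponential dropout (assumed) | 219 | 70.1% |
| 37% removed (assumed) | 218 | 69.9% |

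**Effect of visit-based assessment.** A log-rank simulation (6000 runs, standard error about 0.5 point) dated events to the next SVC visit and censored dropouts at their last visit. It gave 88.5% with no loss, and 85.0%, 81.0% and 74.6% with 20%, 40% and 60% dropout. Dating every event to a visit is a simplification, since death and ventilation are assessed daily. Visit timing does not explain the gap.

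**Other readings of the sentence.**

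- 73% as the overall rate: 86.2%, or 77.8% with 20% removed.
- 73% as the placebo rate: 81.6%, or 72.5% with 20% removed.
- One-sided 5%: 93.1%.
- Two-proportion test of 73% against 84.6% with 20% removed: 70.5%.
- Two-sided alpha of 0.01 with no loss: 70.9%.
- Two-sided alpha of 0.025 with 20% removed: 71.1%.
- No loss but HR 0.75: 70.9%.

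Every variant that lands near 70% contradicts a stated input, the stated test or the stated alpha.

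**The case against.** The best reply is that the sentence does not claim to list every input, so what is shown is a gap in traceability and not a proven miscalculation. Loss mechanisms can also combine. Removing the 20% and censoring a further assumed 20% at randomisation leaves 0.80 × 0.80 = 64% of 346, or 221 events, and 70.6% power. Some baseline censoring is plausible: entry requires sitting SVC of 60–90% of predicted, the event is supine SVC at or below 50%, and there is no supine floor at entry. There are other possible origins too. One is the two-proportion test with 20% removed. Another is the product of 87.8% and the 80% stated for the endpoint ranked above (CAFS), which is 70.3% if the two are independent.

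It is true that the cause cannot be identified from the documents. But the combined case is the same 36–37% loss found above, and its second half has no documented share. The baseline rule appears only in the SAP, while the 70% is already in the protocol. The two-proportion test conflicts with the stated log-rank test, and nothing in the text says that the 70% is a joint power.

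A second point stands in part. The primary population is all randomised subjects, dropouts are censored and not deleted, and SAP 6.2.5 lists this endpoint for multiple imputation. Outright removal to 360 subjects is therefore not the planned analysis, and the 80% should be read as the harshest use of the one stated loss rate. The figure tied directly to the printed inputs is 88%.

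The consequence is also limited. SAP section 5 bases the sample size primarily on supine SVC, and correcting this figure changes no analysis.

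**Conclusion.** The stated power is wrong for its stated inputs. With 73% on levosimendan, HR 0.70, 300/150 subjects and a two-sided 5% log-rank test, power is about 88%. It is 85% with 20% exponential dropout and 80% with 20% removed. If the inputs are right, the plan understates power by about 18 points, or about 10 under the harshest use of the 20%, and the trial is not underpowered for this endpoint on those assumptions. If 70% is what was intended, an input, the test, the alpha or a loss of about 37% of events is mis-stated or undisclosed. The documents do not settle which. The calculation assumes proportional hazards and, for the dropout cases, exponential event and dropout times. This should be corrected, but it does not threaten the design.

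**What to change.** Rerun the calculation and amend the sentence in SAP section 5 and Protocol 8.2 in one of two ways:

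1. Keep 73% and HR 0.70 and restate the power as about 88%. If a loss case is shown, label it: about 80% if only 360 subjects are evaluable.
2. Keep about 70% and state what produces it: event rate in each arm, hazard ratio, test and alpha, loss or censoring assumption (including the share censored at treatment discontinuation and at baseline), and expected number of events.

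At the same time, check whether the interim projections rest on the same inputs. The SAP says "We estimate that approximately 40% and 85% of the respiratory events will have accumulated at the time of the planned interim analyses", while Protocol 8.5 gives about 35% and 75%, yet the power sentence carries the same numbers in both documents.

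The cost is one recalculation and one sentence in each document, with no change to enrolment.

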6. GENERAL STATISTICAL CONSIDERATIONS

6.1 Data sets to be analysed

The intent-to-treat (ITT) population, including all randomized subjects, will be used for the primary evaluation. All subjects who received any study treatment will be included in the evaluation of safety. Sensitivity analyses will include evaluations of key endpoints in the full analysis set (FAS), including all treated subjects with at least a baseline and one post-baseline SVC measurement, and in the per-protocol (PP) population.

The PP population includes all randomized subjects, excluding subjects with important protocol deviations affecting the evaluation of efficacy. The study has two key intervals at which efficacy endpoints are generally evaluated: up to week 12, and up to week 48. For endpoints evaluated at week 12, it would not be desirable to exclude subjects from the PP analyses due to important protocol deviations occurring only after the endpoint has already been assessed. To address this, two separate PP populations will be created: PP up to week 12 (PP1) and PP up to week 48 (PP2). Important protocol deviations occurring before week 12 will lead to exclusion from both populations, while deviations occurring only after the week 12 visit has already been completed will only exclude the subject from PP2. The appropriate PP population will then be chosen for the analyses, according to the endpoint.

The importance of protocol deviations with respect to leading to exclusion from the PP populations will be evaluated during subject classification review meetings with the clinical study team. General principles that lead to exclusion contain: inclusion and exclusion criteria deviations, completeness of key efficacy assessments, use of prohibited medications, compliance and other important protocol deviations; and are detailed in a separate subject classification document.

Subject classification will be completed during the blind review before the database lock and opening of the treatment code.

Analyses of the effects of the COVID-19 pandemic are detailed in section [7.10.3](#).

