6.2.9 Multiple timepoints

The primary efficacy model will include all planned post-baseline visits up to the Week 12 visit. Additional analyses of primary efficacy will include all planned study visits. Included timepoints for other endpoints will be described separately. Baseline measurements of outcome variables will be included as covariates in the models. The MMRM will be used to estimate the covariance between measurements for a given subject, without assuming any specific structure a priori. Planned visit will be included as a factor in the model. For slope analyses, the actual study day of the visit will be used. All time-to-event analyses will be performed up to the first event only.

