7.5.4.2 Per-protocol population

Method:

- Use the appropriate PP population (see [6.1](#)).

Analyses that will be adjusted:

- With PP up to week 12 (PP1):
 - Primary analysis SVC MMRM
 - Supine Borg CR 10 scale at 12 weeks
- With PP up to week 48 (PP2):
 - CAFS through 48 weeks
 - Time to respiratory event
 - CGI through 48 weeks
 - Slope of change in the ALSFRS-R respiratory domain through 48 weeks

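### The per-protocol analysis of time to respiratory event deletes subjects for deviations that occur after their own event; the criteria should stop at the event or censoring date

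*SAP*

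**What the plan says.** SAP 6.1 makes ITT the primary population and uses the per-protocol sets for sensitivity analyses. The per-protocol population is defined by "excluding subjects with important protocol deviations affecting the evaluation of efficacy". The listed grounds cover entry criteria and also "completeness of key efficacy assessments, use of prohibited medications, compliance and other important protocol deviations"; the detail is left to a separate subject classification document. Classification is done blind, before database lock.

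The same section explains why there are two sets. For endpoints assessed at Week 12, it does not want to lose subjects "due to important protocol deviations occurring only after the endpoint has already been assessed". Important deviations before Week 12 remove a subject from both sets, while "deviations occurring only after the week 12 visit has already been completed will only exclude the subject from PP2". The only cut-off is the Week 12 visit.

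SAP 7.5.4.2 assigns time to respiratory event to PP2, together with CAFS, CGI and the ALSFRS-R respiratory slope. On the endpoint itself, SAP 7.5.2.3 says: "Time to respiratory event is reached whenever any of the criteria has first been met". SAP 6.2.9 adds: "All time-to-event analyses will be performed up to the first event only". SAP 6.2.5 and Table 2 censor subjects one day after they stop study treatment.

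**The concern.** CAFS, CGI and the respiratory slope use data up to Week 48, so a 48-week window for deviations fits them. Time to respiratory event differs: each subject's endpoint closes on that subject's own event or censoring date, often well before Week 48. Nothing in SAP 6.1 or 7.5.4.2 ties exclusion to that date.

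Two things follow. Completed, valid events are discarded. Selection into PP2 can also depend on behaviour after the outcome: poorer compliance, a newly started prohibited treatment or missed assessments may all follow respiratory decline. Most of the component events (a one-point ALSFRS-R respiratory decline, supine SVC at or below 50% predicted, starting NIV) do not oblige the subject to stop study treatment, so later deviations are possible. If post-event deviations are more frequent in one arm, more of that arm's events are removed, and its hazard looks lower than it is.

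The endpoint is second in the secondary testing hierarchy, so its per-protocol result is likely to be read as support for, or doubt about, the ITT result.

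**Working it through.** **1. The rule applied to one subject.** Event at Week 10, important deviation at Week 30. Under 6.2.9 and 7.5.2.3 the endpoint is complete at Week 10. Under 6.1 the Week 30 deviation removes the subject from PP2. Under 7.5.4.2 the Week 10 event is therefore absent from the per-protocol analysis. This step needs no assumption.

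**2. Inputs.** SAP section 5 gives a 48-week event rate of 73% on levosimendan, a hazard ratio of 0.70, 450 subjects randomised 2:1, and power of about 70% by log-rank test. The implied placebo rate is 1 − 0.27^(1/0.70) = 84.6%.

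**3. The plan's own figure.** Events = 300 × 0.73 + 150 × 0.846 = 346. Schoenfeld: √(346 × 2/3 × 1/3) × |ln 0.70| − 1.96 = 1.17, which gives power of 87.8%. With 360 evaluable subjects (277 events) it is 79.9%. The stated 70% is not reproduced. That is a separate matter; only the event rate and hazard ratio are used below.

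**4. Share of post-Week-12 deviators who already had the event.** Assume exponential event times, follow-up to Week 48, and deviations unrelated to the event.

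- λ(levosimendan) = −ln(0.27)/48 = 0.0273 per week; λ(placebo) = 0.0273/0.70 = 0.0390 per week.
- Share at deviation time t is 1 − exp(−λt). Weighted 2:1, it is 31% at Week 12, 52% at Week 24, 67% at Week 36 and 77% at Week 48. It passes 50% at about Week 22.5.
- With deviations uniform over Weeks 12–48, the mean is 1 − [exp(−12λ) − exp(−48λ)]/(36λ): 54% on levosimendan, 66% on placebo, and (2 × 54 + 66)/3 = 58% pooled.
- Variations on the uniform case: 42% if all deviations fall in Weeks 12–24; 46% if 73% is read as the placebo rate; 45% or 35% (simulated) if subjects leave after the event at 3% or 6% per week; 71% or 77% (simulated) if the deviation rate doubles or triples after the event.

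**5. Effect on the hazard ratio.** Simulation with exponential event times and a pre-event deviation hazard of 0.3% per week from Week 12. PP2 deletes anyone with a deviation before Week 48.

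| Deviation rate after the event | PP2, true HR 1.00 | PP2, true HR 0.70 |
|---|---|---|
| Unchanged in both arms | 1.00 | 0.70 |
| Tripled in both arms | 1.00 | 0.69 |
| Tripled on levosimendan only | 0.90–0.92 | 0.63 |
| Tripled on placebo only | 1.10 | 0.76–0.77 |

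Ranges reflect separate simulation runs. Censoring at the first deviation gave about 1.00 and 0.70 in every row. The one-arm rows exclude about 20% of one arm and 10% of the other. A higher base rate enlarges the shifts: at the rate that excludes 20% when deviations are unrelated to the event (−ln(0.80)/36 = 0.62% per week), tripling in both arms gives 0.68.

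**6. A remedy that does not work.** Deleting only subjects whose deviation precedes the event turns 0.70 into about 0.71 even when deviations are unrelated to the event. A later event leaves more time to deviate first, so this rule selects on event time.

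**The case against.** The strongest reply is that little depends on this analysis. ITT is primary, the per-protocol analysis is one of eleven listed sensitivity analyses, no decision rule uses it, and only important deviations that affect the evaluation of efficacy count. All of that stands and sets the weight of the point. Blinded classification also guards against deliberate selection, but it does not remove dependence on the outcome, because post-event conduct is still what is being classified.

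Four stronger readings are tempting, and the documents do not support them.

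- *That most post-Week-12 exclusions concern subjects already past their event.* The documents give no number, timing or event status for deviations. The 73% is cumulative at Week 48, and the share falls below half under several reasonable assumptions.
- *That SAP 6.1 contradicts itself.* Its stated principle is limited to Week 12 endpoints. Applying it to an event-driven endpoint is a reasonable extension, but the SAP does not commit itself to it.
- *That death or intubation would itself count as incomplete assessment and so cause exclusion.* Stopping treatment at intubation or tracheostomy follows Protocol 4.5 and is not a deviation. Nothing says that assessments missed for such reasons count, and the classification document is not available.
- *That the per-protocol analysis cannot inform the ITT result.* The larger shifts require post-event deviations to triple in one arm alone, and no figure in the documents supports that.

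**Conclusion.** The point holds as a gap in the rule. As written, PP2 drops a subject from time to respiratory event for an important deviation after that subject's own event, and nothing in either document prevents it. The unseen classification document might.

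The share of exclusions affected is unknown. Around half is a fair working figure under the SAP's event assumptions, exponential times and evenly spread deviations, with roughly 31% to 77% as the range by timing. If deviations are unrelated to the event, data are lost but the hazard ratio is unbiased. A post-event rise shared by both arms moves 0.70 by about 0.01 (0.02 at the higher base rate) and leaves 1.00 unchanged. A move of about 0.07 is an assumed extreme, not an expectation.

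This is a cheap improvement to a sensitivity analysis. It does not affect the primary analysis of this endpoint.

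**What to change.** In SAP 6.1 and 7.5.4.2, and in the subject classification document, add for the per-protocol analysis of time to respiratory event:

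- Important deviations after the subject's event or censoring date are disregarded. This also settles how assessments missed after the event are treated.
- When the first important post-baseline deviation precedes the event, the subject is censored at the deviation date instead of being deleted. This includes deviations before Week 12.
- Entry-criteria deviations still remove the subject entirely.

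Do not simply delete the pre-event deviators, for the reason in step 6 of the working.

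The cost is one paragraph; deviation timing is already needed to separate PP1 from PP2. There are two downsides. The per-protocol set for this endpoint will differ from PP2 for the other 48-week endpoints. Censoring at the deviation also assumes that pre-event deviations are unrelated to prognosis. When they were tied to prognosis and made more frequent in one arm (lognormal frailty, SD 1), censoring gave about 0.98 against a true 1.00. That bias is small, but the SAP should state the assumption.
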